2.13 Interim analysis

Not applicable.

3 Sample size calculation

The sample size is determined as precision-based for the change from baseline in MMSE score at week 24. Ninety-seven patients will ensure that the half-width of 95% confidence interval for the change from baseline in MMSE score at week 24 would be 0.6, assuming SD=3.0 which is estimated from 1301, 1303 and 1403 studies. Assuming drop-outs, a total of 120 patients will be enrolled to achieve at least 97 evaluable patients.

4 Change to protocol specified analyses

The following are considered for the analysis which was not planned during the time of protocol development:

1. Rate of responses for change from baseline in MMSE total score has been provided based on Full Analysis Set, Per Protocol Set and subjects with 3-step titration.
A responder is defined as those patients whose MMSE total score has remained unchanged from baseline till Week 24 or, patients whose MMSE total score has improved at Week 24 compared to baseline.
2. For Neuropsychiatric Inventory (NPI), the value 0 is considered wherever N/A or Absent has been marked in the eCRF page.
3. Visit Window for discontinuations: The study does not have a pre-defined visit windows for the entire study period. However, correct visit re-mapping for the discontinued patients was performed for summarizing and listing the efficacy and safety variables by visits. The last records of the discontinued patients are re-mapped to the actual visit when they discontinued rather than the Visit 8/discontinuation as per the assessment schedule of the protocol. Re-mapping was done for the discontinued patients to the nearest planned visit as per their actual discontinuation/ assessment date for each variable.

The following efficacy assessments: MMSE, NPI-10, QOL-AD, J-CGIC and Modified Crichton Scale were re-mapped for the considered discontinued patients as described above.

Under safety assessment, Vitals were considered for re-mapping for the discontinuation patients as described above. For other safety assessments, this re-mapping had no impact.

5 Appendix

This appendix gives details about statistical methods in addition to the report text. All analyses will be performed by using SAS version 9.4.

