(b) Imaging test can be performed at screening visit if latest imagings of a patient are more than 3 years old from baseline.

(c) Based on answer of questionnaire from the caregiver

(d) Based on the interview and assessment by investigators

(e) These assessments are not mandatory at discontinuation due to adverse events

(f) During the screening period, patients will continue receiving their previous medication (donepezil or galantamine)

(g) At the baseline visit, patients discontinue their previous ChE inhibitors (donepezil, galantamine) and could start the initial dose of 9 mg/day rivastigmine patch after cleared all necessary assessment for enrollment. If patients already take their previous ChE inhibitors on the day of baseline visit, the patients should start the initial dose of 9 mg/day rivastigmine patch on the following day (Day 1).

(h) If a patient discontinues the study, scheduled assessment should be performed as soon as possible, but visit window is not set.

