### **6.4.1 Mini-Mental state examination (MMSE)**

MMSE will be conducted at Visit 1, 2, 4 and 8 (refer [Table 6-1](#)). MMSE at premature discontinuation will not be conducted if patient discontinues because of adverse event.

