2.5.3 Handling of missing values/censoring/discontinuations

The primary analysis will be performed using a MMRM model, which assumes that missing data is missing at random (MAR) given the preceding observed data.

The discontinuations data has been handled as explained in Section 4, point 3. No other imputation methods will be considered.

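### Does the loosely worded re-mapping of discontinuation visits in SAP Section 4 leave the primary MMRM unreproducible or unable to run?

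*SAP*

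**What the plan says.** The primary analysis is an MMRM of MMSE change with visit, baseline MMSE and an unstructured covariance (SAP 2.5.2, code in 5.3.1). On dropouts, SAP 2.5.3 says: "The discontinuations data has been handled as explained in Section 4, point 3". Section 4, point 3 then makes three statements:

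- On windows: "The study does not have a pre-defined visit windows for the entire study period".
- On the target: "The last records of the discontinued patients are re-mapped to the actual visit when they discontinued rather than the Visit 8/discontinuation".
- On the method: "Re-mapping was done for the discontinued patients to the nearest planned visit as per their actual discontinuation/ assessment date for each variable".

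MMSE is among the scales listed as re-mapped, with NPI-10, QOL-AD, J-CGIC and the Modified Crichton Scale. Protocol 6.4.1 sets the MMSE schedule: "MMSE will be conducted at Visit 1, 2, 4 and 8". Protocol Table 6-1 gives a window for each scheduled visit (Visit 4: Days 49 to 63; Visit 8: Days 161 to 182). Its footnote (h) covers the exception: "If a patient discontinues the study, scheduled assessment should be performed as soon as possible, but visit window is not set". Footnote (e) says of the efficacy scales: "These assessments are not mandatory at discontinuation due to adverse events".

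**The concern.** The rule feeds the primary analysis, yet its wording allows two constructions. The candidates may be all planned visits or only those where the scale is due. Two programmers could therefore build different Week 24 data sets. Nothing says what happens when a date is equally far from two visits, or when a re-mapped score falls on a visit that already has one. The second gap matters more. A patient with a Visit 4 MMSE and a discontinuation MMSE mapped to Week 8 would have two records at one level of the repeated effect, and the model in SAP 5.3.1 could not be fitted. Someone would then have to choose a value in an open-label study. The added responder rate in SAP Section 4, point 1, which counts "patients whose MMSE total score has improved at Week 24 compared to baseline" as well as unchanged patients, rests on the same mapping. The sentence on windows is also inaccurate for scheduled visits.

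**Working it through.** **Planned precision.** SD 3.0 and half-width 0.6 (Protocol 9.8, SAP Section 3): n = (1.96 × 3.0 / 0.6)² = 96.04, rounded up to 97, as stated. The plan enrols 120, so it allows for 120 − 97 = 23 dropouts.

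**Where Week 24 starts.** Planned days are 28, 56, 84, 112, 140 and 168 (Table 6-1).

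- All planned visits: (140 + 168)/2 = 154 is a tie, so Week 24 starts on Day 155. Week 8 takes Days 43 to 69.
- MMSE visits only: (56 + 168)/2 = 112 is a tie, so Week 24 starts on Day 113, which is 161 − 113 = 48 days before the Visit 8 window opens. Week 8 runs to Day 111.

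**How many records.** Protocol 6.4.1 says no MMSE is done at discontinuation for an adverse event, and Protocol 5.6.3 rules out assessments after consent withdrawal. The documents do not give the number left. If the earlier 1-step group's rate of adverse-event discontinuation (16/107, Protocol 1.1) carried over, 16/107 × 120 = 17.9, leaving about 5 of 23. This is an assumption; footnote (e) would let the number be higher.

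**Effect on the Week 24 mean.** Assume 5 records evenly spread over Days 2 to 160 (159 days), each 2 to 3 points away from what the model would otherwise imply. With k early records labelled Week 24, the shift is k/(97 + k) × 2 to 3.

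- Day 113 start: k = 48/159 × 5 = 1.51; shift = 1.51/98.51 × 2 to 3 = 0.03 to 0.05 points, 5 to 8% of 0.6.
- Day 155 start: k = 6/159 × 5 = 0.19; shift = 0.19/97.19 × 2 to 3 = 0.004 to 0.006 points, 1% or less of 0.6.

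The responder rate moves by at most 1.51/98.51, about 1.5 percentage points, with the Day 113 start.

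**Duplicates.** Two records at one visit share variance 9 and covariance 9, so the determinant is 9 × 9 − 9 × 9 = 0 and the likelihood cannot be evaluated. A simulated REML fit with one such patient stopped at its starting values and ran without that patient; SAS itself was not run. With Visit 4 on Day 56, the exposed days are 57 to 111 (55 days) or 57 to 69 (13 days). The expected number of duplicates is 55/159 × 5 = 1.7 or 13/159 × 5 = 0.4. The chance of at least one is 1 − (104/159)⁵ = 88% or 1 − (146/159)⁵ = 35%. If the choice between two scores changed a patient's Week 8 value by 3 points, the Week 8 mean would move by about 1.7 × 3/97 = 0.05. Week 24 is affected only through the correlation between visits.

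**What the rest of the plan settles.** SAP 2.1.1.4 computes change at scheduled visits. SAP 2.2.1.1 names Week 8 and Week 24 as the post-baseline MMSE visits, and SAP 2.6.1.1 plots those two. So the visit factor for MMSE has two levels, even though SAP 5.3.1 defines it in general terms. Point 3 also lists QOL-AD as re-mapped. QOL-AD has only Visit 8 after baseline, so re-mapping could not move it unless all planned visits are candidates. That, with the reference to the actual visit, favours the Day 155 start. This is an inference; the SAP does not state it.

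**The case for a change.** The best case for acting is that the rule governs the primary endpoint, each reading has some textual support, and a duplicate is not remote (88% or 35% above). A late choice of record in an open-label study is better avoided, and a few sentences would prevent it. If all 23 planned dropouts had a discontinuation MMSE, the Day 113 start would give k = 48/159 × 23 = 6.94 and a shift of 0.13 to 0.20 points, up to a third of the half-width.

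The omission stands, and so does the inaccuracy about windows, which is true only of the discontinuation visit. The rest is weaker. The 23-patient case requires an MMSE from every dropout, against Protocol 6.4.1 and 5.6.3. The code in SAP 5.3.1 reads a placeholder data set, so record selection happens before it and the code neither requires nor allows duplicates. Point 3 is in the past tense, so any duplicate would already have been met and resolved.

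A stricter rule is not clearly better. Admitting discontinuation scores only inside the Table 6-1 windows would, with even timing, remove (159 − 15)/159 = 91% of them from a model that relies on missingness at random and is meant to include all FAS patients (SAP 2.5.1).

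**Conclusion.** The SAP leaves out detail that analysts fill sensibly, and the Week 24 estimate does not depend materially on how they fill it. Moving a dropout's last score out of Visit 8 is sound in itself. The other sections limit the MMSE model to two visits. Keeping one record per patient and visit is ordinary data-set construction, and failing to do so would halt the program, not produce a wrong number. On the stated assumptions (about 5 discontinuation scores, even timing, 2 to 3 points off), the shift is 0.05 points or less against a half-width of 0.6. P-values are descriptive, and the completer and LOCF analyses in SAP 2.5.4 show the result under other treatments of the same patients. The judgement would weaken if far more dropouts had a discontinuation MMSE and the Day 113 start was used. No change to the plan follows.

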2.1.1.4 Post-baseline assessments

Post-baseline values are defined as assessments taken after the start of study treatment.

When change from baseline is of interest the following formula will be used for each scheduled visit and time-point where baseline and post-baseline values are both available: **Change from baseline = post-baseline value – baseline value.**

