2.8.1.1 QOL-AD score

The QOL-AD is a brief, 13-item measure designed to obtain a rating of the patient's Quality of Life from the caregiver. A lower score indicates more severe impairment.

The change from baseline at Week 24 in the QOL-AD total and sub-item scores (by patients or caregivers) will be summarized along with 95% confidence interval of the mean for the FAS. Assessment of QOL of a given patient by his/her caregiver should be considered as primary measurement while assessment of QOL of a given patient by his/herself will be recorded as reference.

In addition, association between QOL-AD total score and each of MMSE total score, NPI-10 total score, J-CGIC and Modified Crichton Scale total score will be explored. A logistic regression will be considered to select the appropriate factors and thereafter to test whether or not the selected factors are associated with QOL-AD.

Similarly, the association between QOL-AD and number of gastrointestinal AEs and Application skin AEs will be explored using a regression analyses.

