2.10.1.1 J-CGIC

J-CGIC is a global assessment scale to assess change of the patient's clinical symptoms, which are assessed subjectively by clinicians with seven grades. (1: Marked improvement, 2: Moderate improvement, 3: Mild improvement, 4: Unchanged, 5: Mild Worsening, 6: Moderated Worsening, 7: Marked Worsening). The number and percentage of patients in each grade will be displayed at visits 3, 4, 6 and 8. Also, proportion and 95% confidence interval for the proportions of the patients without worsening (1: Marked improvement, 2: Moderate improvement, 3: Mild improvement, 4: Unchanged) and with improvement (1: Marked improvement, 2: Moderate improvement, 3: Mild improvement) will also be provided.

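### Does the SAP need a stated denominator for the Week 24 responder rate and J-CGIC proportions once exit scores are re-mapped?

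*SAP*

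**What the plan says.** Under the protocol's Table 6-1, Visit 8 doubles as the discontinuation visit. SAP Section 4, point 3, separates the two. Last records of discontinued patients are "re-mapped to the actual visit when they discontinued rather than the Visit 8/discontinuation as per the assessment schedule of the protocol", and the visit is chosen by date: "Re-mapping was done for the discontinued patients to the nearest planned visit as per their actual discontinuation/ assessment date for each variable". The scales are named: "The following efficacy assessments: MMSE, NPI-10, QOL-AD, J-CGIC and Modified Crichton Scale were re-mapped".

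Three Week 24 results are affected.

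- **MMSE responder rate** (SAP Section 4, point 1), an analysis added after the protocol: "Rate of responses for change from baseline in MMSE total score has been provided based on Full Analysis Set", with the per-protocol set and the 3-step patients as further sets. A responder has an unchanged MMSE or is among "patients whose MMSE total score has improved at Week 24 compared to baseline".
- **J-CGIC** (SAP 2.10.1.1): "The number and percentage of patients in each grade will be displayed at visits 3, 4, 6 and 8", with proportions and 95% intervals for patients improved and for patients not worsened.
- **QOL-AD** (SAP 2.8.1.1): change at Week 24, which "will be summarized along with 95% confidence interval of the mean for the FAS".

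SAP 2.1.1.4 computes change from baseline "for each scheduled visit and time-point where baseline and post-baseline values are both available". The missing-data text in SAP 2.5.3 and the completer and LOCF t-tests in 2.5.4 concern the MMSE mean change only.

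**The concern.** The FAS requires a baseline and any post-baseline assessment on treatment, so it can include patients with no Week 24 score. For the responder rate, naming the FAS suggests that every FAS patient is in the denominator and that a patient without a Week 24 score is a non-responder. The rate is also described as one of change from baseline, and SAP 2.1.1.4 computes change only when both values exist, which suggests observed cases. J-CGIC has no denominator stated at all. Two programmers could follow the SAP and print different percentages. The observed-case figure is never the lower one, because it leaves the drop-outs out.

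QOL-AD raises a further question, since its only post-baseline visit is Visit 8. If the nearest planned visit means the nearest visit at which the scale is scheduled, re-mapping never moves a QOL-AD score. If it means any study visit, most exit scores leave the only QOL-AD change analysis.

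The study is open-label with one arm, and Section 4 is partly in the past tense. An open choice of denominator could therefore be made with the data in view.

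**Working it through.** **Inputs.** SD 3.0, half-width 0.6, 97 evaluable of 120 enrolled (SAP Section 3). AE discontinuation 16/107 = 15.0% in the earlier 1-step arm (Protocol 1.1 and 3.6). Visit days from Protocol Table 6-1. Assumed, because the documents do not give them: mean MMSE change between 0 and -1, FAS of 110 to 120, QOL-AD SD of 5.

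**The plan's own figure.** n = (1.96 × 3.0 / 0.6)² = 96.04, rounded up to 97, which agrees. The implied loss is 23/120 = 19.2%.

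**Responder rate.** With whole-number scores, a responder has change ≥ 0, approximated by P(X > -0.5) with X normal and SD 3.0.

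| Mean change | Observed cases | FAS 120 (× 97/120 = 0.81) | FAS 110 (× 97/110 = 0.88) |
|---|---|---|---|
| 0 | 56.6% | 45.8% | 49.9% |
| -0.5 | 50.0% | 40.4% | 44.1% |
| -1 | 43.4% | 35.1% | 38.3% |

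The gap is 8 to 11 points at FAS 120 and 5 to 7 points at FAS 110. The 95% half-width at n = 97 is 1.96 × √(p(1-p)/97), about 10 points.

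**J-CGIC.** The same factors apply. An observed 60% becomes 0.60 × 97/120 = 48.5% or 0.60 × 97/110 = 52.9%. At a higher rate the gap grows: 68/97 = 70.1% against 68/120 = 56.7%, or 13 points.

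**How much is due to the re-mapping.** At the earlier AE rate, 120 × 16/107 ≈ 18 of the 23 leave for AEs. Protocol 6.4 says their exit efficacy assessments are not done (Table 6-1, note e, says not mandatory). That leaves about 23 - 18 = 5 exit scores to move. If all five stayed at Week 24 as non-responders, the top rate would go from 56.6% to 56.6% × 97/102 = 53.8%, under 3 points. The rest of the gap comes from patients with no score to move.

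**QOL-AD.** If any study visit counts, a score stays at Week 24 from Day 155, since the midpoint of Days 140 and 168 is Day 154. With exits spread evenly, 154 of 168 days (92%) fall earlier. With e exit scores, of which a = 14e/168 stay, the weight that moves is e/(97+e) - a/(97+a). For e = 5 this is 0.0447. If exit scores are 3 points worse (assumed), the mean shifts 0.13 against a half-width of 1.96 × 5/√97 = 1.0. The ceiling, all 23 with an exit score, is 0.52.

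**Primary model.** SAP 2.2.1.1 names Week 8 and Week 24 as the post-baseline MMSE visits. An exit on Days 57 to 69 could coincide with a scheduled Week 8 score: 13/168 × 5 = 0.4 patients, or 1.8 if all 23 had exit scores. In a simulated two-visit model (correlation 0.6 assumed, exit scores 2 points lower), the Week 24 mean shifts by -0.006 with 5 exit scores and -0.024 with 23.

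**The case for a change.** The strongest case for a change is that a gap of up to about one confidence-interval half-width can arise from the same SAP text, always in one direction and with no control arm to offset it. The responder rate was added after the protocol, so pre-specification was its main protection. The SAP does give item-level rules for NPI-10 and the Modified Crichton Scale, so silence here stands out, and a few words would settle it.

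The silence on the denominator stands, and so does the doubt about which planned visit is nearest for QOL-AD. The rest weakens on inspection.

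- The upper-end gap needs an FAS of 120 with exactly 97 observed. The SAP plans for at least 97, so with 120 enrolled 23 missing is the planning maximum.
- The text contains no rule that gives a wrong answer. Observed cases with their N, and all FAS patients with missing counted as non-response, are both accepted ways to report a descriptive proportion. Statisticians could reasonably differ on which to put first.
- Little stays hidden. SAP 2.1 reports categorical variables as number and percentage, so the denominator can be recovered, and SAP 2.3.1 reports discontinuations with reasons. A reader can turn 48/97 = 49.5% into 48/120 = 40.0% by hand.
- QOL-AD is not without a rule. SAP 2.1.1.4 makes its mean an available-case mean, and naming the FAS does not promise imputation.

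**Conclusion.** No change to the plan follows. This is missing detail that analysts can fill sensibly. The re-mapping itself is a reasonable, disclosed step that stops an early exit score from being reported as Week 24.

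The denominator choice could move the responder rate or a J-CGIC proportion by about 5 to 13 points. That range rests on 97 observed Week 24 values, an FAS of 110 to 120 and observed rates of roughly 43% to 70%. Only about 5 of the 23 planned losses would have an exit score to re-map, if the earlier 15.0% AE rate holds and AE leavers have no exit assessment.

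The stakes are low. The responder rate is not in the endpoint table of SAP 1.2, and J-CGIC is a descriptive secondary endpoint. Protocol 3.2 disclaims any superiority or non-inferiority aim, and the MMSE p-values are descriptive. The primary estimate moves by about 0.02 points at most against 0.6. The QOL-AD mean moves by 0.13 against 1.0 under the assumed SD and deficit, with a ceiling of 0.52.

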5.1 Imputation rules

1. Adverse events

AE START DATE IMPUTATION (CENA713D2340)

where AE start date is XX-MON-YYYY and Treatment start date is XX-TRTM-TRTY,

If YYYY<TRTY and MON missing, then AE start date=1-JULY-YYYY which is prior to start of trt

If YYYY<TRTY and MON<TRTM, then AE start date=15-MON-YYYY which is prior to start of trt

If YYYY<TRTY and MON=TRTM, then AE start date=15-MON-YYYY which is prior to start of trt

If YYYY<TRTY and MON>TRTM, then AE start date=15-MON-YYYY which is prior to start of trt

If YYYY=TRTY and MON missing, then AE start date=TRTSTD+1

If YYYY=TRTY and MON<TRTM, then AE start date=15-MON-YYYY which is prior to start of trt

If YYYY=TRTY and MON=TRTM, then AE start date=max (1-MON-YYYY, TRTSTD+1)

If YYYY=TRTY and MON>TRTM, then AE start date=max (1-MON-YYYY, TRTSTD+1)

If YYYY>TRTY and MON missing, then AE start date=1-JAN-YYYY

If YYYY>TRTY and MON<TRTM, then AE start date=max (1-MON-YYYY, TRTSTD+1)

If YYYY>TRTY and MON=TRTM, then AE start date=max (1-MON-YYYY, TRTSTD+1)

If YYYY>TRTY and MON>TRTM, then AE start date=max (1-MON-YYYY, TRTSTD+1)

AE END DATE IMPUTATION (CQVA149A2340)

AE end date = min (last visit date, last know date of contact for discontinued patients, DEC 31, date of death), if MON is missing and YYYY is present.

AE end date = min (last visit date, last know date of contact for discontinued patients, last day of the Month, date of death), if day is missing, MON and YYYY present.

Impute Date Flag (CQVA149A2340)

If not a complete date:

- If year of the imputed date \neq YYYY then date flag = Y (not possible since missing dates will not be imputed),
- else if month of the imputed date \neq MON then date flag = M,
- else if day of the imputed date \neq day of original date then date flag = D,
- else date flag = null.

2. Concomitant medication

CM start date imputation

Rules for imputing the CMD start date:

Here TRTSTDT = treatment start date,

1. If the CMD start date year value is missing, the imputed CMD start date is set to TRTSTDT-1, if not after the CMD end date. Thus the imputed CMD start date = minimum (TRTSTDT-1, CMD end date).
2. If the CMD start date year value is **less** treatment start date year value, the CMD started before treatment start. Therefore:
 - a) If the CMD year is less than treatment start year and the CMD month is missing, the imputed CMD start date is set to 01JulYYYY.
 - b) Else if the CMD year is less than the treatment start year and the CMD month is not missing, the imputed CMD start date is set to 15MONYYYY.
3. If the CMD start date year value is **greater** than treatment start date year value, the CMD started after treatment start. Therefore:
 - a) If the CMD year is greater than the treatment start year and the CMD month is missing, the imputed CMD start date is set to 01JanYYYY.
 - b) Else if the CMD year is greater than the treatment start year and the CMD month is not missing, the imputed CMD start date is set to 01MONYYYY.
4. If the CMD start date year value is **equal** to treatment start date year:
 - a) If the CMD month is missing or the CMD month is equal to treatment start month, then the imputed CMD start date is set to the minimum (TRTSTDT-1, CMD end date).
 - b) Else if the CMD month is less than the treatment start month, the imputed CMD start date is set to 15MONYYYY.
 - c) Else if the CMD month is greater than the treatment start month, the imputed CMD start date is set to 01MONYYYY.

CMD end date imputing:

1. If the CMD end date is completely missing (and "Ongoing at final examination" was not answered "Yes"), the CMD end date will be the maximum of treatment end date +1 day and CMD start date.
2. If a partial CMD end date is reported (day is missing or day and month are missing), the CMD end date will be imputed by the maximum possible date, i.e.,
 - the end of the reported month if day is missing, or

- the end of the reported year if day and month are missing provided that the imputed date is not before the CMD start date,
- otherwise CMD end date will be equal to CMD start date.

3. CMTIME since first symptoms of AD noticed by patient/caregiver (in years), for the partial dates in the data, the dates will be imputed as:

- If month and year are present, the 1st of the month is considered as the date. For example, if March 2015 is present, it will be imputed as 1st March 2015.
- If only year is present, January will be considered as the month and 1st as the date. For example, only 2015 is present, it will be imputed as 1st January 2015.

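### Partial dates of first AD symptoms are set to the earliest possible date, so the reported time since first symptoms is biased upward, by about half a year on average for each year-only date

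*SAP*

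**What the plan says.** SAP 5.1 (Imputation rules), item 3, concerns time "since first symptoms of AD noticed by patient/caregiver (in years), for the partial dates in the data, the dates will be imputed as" follows. Two rules are given.

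- Day missing: "If month and year are present, the 1st of the month is considered as the date".
- Day and month missing: "If only year is present, January will be considered as the month and 1st as the date". The SAP's example leaves no doubt: "For example, only 2015 is present, it will be imputed as 1st January 2015".

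The same section treats other incomplete start dates differently when the reported year is before the treatment year. For adverse events: "If YYYY<TRTY and MON missing, then AE start date=1-JULY-YYYY which is prior to start of trt". For medications: "If the CMD year is less than treatment start year and the CMD month is missing, the imputed CMD start date is set to 01JulYYYY". When the month is known, both rule sets use the 15th. The SAP gives no reason for the different choice in item 3.

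Protocol 6.2 lists the date of disease onset among the baseline items to be collected. SAP 2.3 has all baseline characteristics summarised for the FAS in the study report.

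**The concern.** Imputing an onset date to the first day of the period in which it is known to lie gives an error that goes one way only. Such errors do not cancel across patients, and a larger sample does not reduce them. What is at stake is one line of the baseline table. It deserves a remark because the trial has a single arm and no comparator (protocol 3.1 and 3.4), so readers judge who was studied from the baseline description, and there is no second arm in which the same offset would cancel.

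**Working it through.** The plan states no figure for disease duration or its error, so there is nothing of its own to reproduce.

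**Inputs.** The imputation rules are those of SAP 5.1. The example year is 2015, the SAP's own, with 365 possible onset days. The documents give no distribution of onset dates, so onset is assumed uniform within the known period.

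**Formula.** Overstatement in years = (true onset date − imputed date) / 365.25. The end date of the interval drops out.

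**Year-only dates, SAP rule (1 January).** The true date lies 0 to 364 days after the imputed date.

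- Mean: 182 / 365.25 = 0.498 years.
- Range: 0 to 364 / 365.25 = 0.997 years.
- About half of the possible onset days give an error between 0.25 and 0.75 years.

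**Year-only dates, 1 July instead.** 1 July is 181 days after 1 January.

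- Mean: (182 − 181) / 365.25 = 0.003 years.
- Range: −0.50 to +0.50 years.
- The mean absolute error falls from 0.50 to 0.25 years.

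**Day missing, month and year known.** Averaged over the days of 2015, the first of the month overstates duration by 0.040 years (about 15 days). The 15th gives 0.002 years.

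**Effect on the reported mean.** Shift = share of year-only dates × 0.498 years. The share is not in the documents, so the values below are assumptions.

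| Assumed share year-only | Shift, 1 January | Shift, 1 July |
|---|---|---|
| 10% | +0.05 years | 0.00 |
| 25% | +0.12 years | 0.00 |
| 50% | +0.25 years | 0.00 |
| 100% | +0.50 years | 0.00 |

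**Onset year equal to the treatment year.** Onset must then precede the start of treatment, so the error is smaller. For assumed starts the mean overstatement is 29 / 365.25 = 0.08 years (1 March), 75 / 365.25 = 0.21 years (1 June) and 121 / 365.25 = 0.33 years (1 September). For the first two starts, an uncapped 1 July would fall after treatment had begun.

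**Where the variable is used.** The primary model (SAP 2.5.2 and 5.3.1) contains visit and baseline MMSE. Time since first symptoms is not among the efficacy or safety subgroups (SAP 2.2.1), the eligibility criteria (protocol 4.1 and 4.2), the sample-size inputs (SAP 3) or the exclusion rules for the analysis sets (SAP 5.2).

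**The case against.** The strongest reply is that item 3 is a clear, deterministic convention with worked examples, so two programmers would obtain the same result. The adverse event and medication rules serve another purpose: they place an event before or after the start of treatment and do not estimate a duration. Nor does SAP 5.1 follow a general midpoint policy. It uses 1 January for year-only adverse event and medication starts after the treatment year, the latest possible date for partial medication end dates, and dates tied to treatment start for year-only starts in the treatment year.

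All of that stands. A reader might infer that the SAP contradicts itself, but it does not. The midpoint rules for years before the treatment year are a precedent for the fix, not a standard that item 3 breaks.

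Two further inferences also fail. One is that onset dates are mostly known by year only, so that many patients are affected; the documents say nothing about how often this happens. The other is that disease duration defines the population that failed earlier treatment. Protocol 1.2 and 4.1 define failure by MMSE decline, worsening of behaviour or daily function, or difficulty with oral treatment. The documents also do not say how other studies impute onset dates, so a gain in comparability between studies cannot be shown.

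The reply leaves the bias itself untouched. For a descriptive duration there is no evident reason to prefer the earliest date, and the SAP offers none.

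**Conclusion.** The point holds as a small, inexpensive improvement. Under item 3 the time since first symptoms is biased upward, on average by about 0.5 years per year-only date and 0.04 years per date lacking only the day. Both figures rest on uniform onset within the period. The shift in the reported mean is 0.05 to 0.50 years for assumed year-only shares of 10% to 100%.

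It would be wrong to read this as an error of half a year in every such patient. Half a year is an average: individual errors run from 0 to just under 1 year, and they are smaller when the onset year is the treatment year. It would also be wrong to infer any effect on the trial's conclusions. In the text that can be read, the variable enters no efficacy estimate, confidence interval, p-value, analysis set or safety output.

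**What to change.** In SAP 5.1, item 3, impute 1 July when only the year of first symptoms is known and the 15th when only the day is missing. Add that the imputed date may not be later than the date of diagnosis, where known, or Day 1.

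The midpoints agree with the SAP's own start-date rules for years before the treatment year. The cap is an addition, needed mainly when the onset year is also the year of diagnosis or treatment. It prevents impossible durations but does not itself remove bias in those few cases.

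The cost is a short change to the SAP text and a few lines of code, including a condition for incomplete diagnosis dates. If the sponsor prefers to keep the earliest date, the SAP should give the reason, and the baseline table should report how many onset dates were year-only and how many lacked only the day, so that readers can judge the offset.
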